### **5.21o Brief COPE**

The Brief COPE is a 28-item measure developed to assess a broad range of coping responses. The Brief COPE has been validated in several populations including breast cancer patients and community samples. Subscales of the Brief COPE include use of emotional support, religion, and self-distraction, and individual subscales can be used independently. We will use the denial, behavioral disengagement, self-distraction, active coping, use of emotional support, use of instrumental support, positive reframing, planning, acceptance, and religion subscales of the Brief COPE. The Brief COPE will be administered to patients during the participant baseline interview (Appendix C).

### **5.21p Note on Smartphone Surveys**

The PHQ-9 is not administered through the smartphone application—only during baseline and post-baseline surveys, which are administered by a research assistant—so the study team will become aware of any concerning responses to PHQ-9 items immediately. We will review the symptom surveys administered over Beiwe daily and have developed an automated internal reporting tool for this purpose. The audio recordings will be reviewed at the end of the study, and patients will be notified that the recordings will not be reviewed in real-time by a clinician when they are taught how to use the smartphone app. Additionally, after each symptom survey, patients are automatically reminded that a clinician will not see their responses in real-time and that they must contact their clinicians with concerns.

**Table 1. Distribution of measures during Phase 1 and Phase 2**

	INSTRUMENTS 				
	Participant Baseline Interview		Participant Post-Baseline Interview		Clinician Survey
	Phase 1	Phase 2	Phase 1	Phase 2	
MEASURE	PRO-CTCAE	✓	✓	✓	✓
	PROMIS Global-10 and Physical Function 6b	✓	✓	✓	✓
	CTCAE				✓
	ECOG PS	✓	✓	✓	✓
	PHQ-9	✓	✓	✓	
	GAD-7	✓	✓	✓	
	EQ-5D-5L	✓	✓	✓	✓
	FACIT-PAL	✓	✓	✓	
	Brief COPE		✓		
	Health Literacy & Numeracy	✓	✓		
	Cancer Experience Question		✓		✓
	Mobile Communication Competence	✓	✓		
	Smartphone Usage Questions	✓	✓		
	Demographic Info	✓	✓		

 Measures were refined during phase I, resulting in the addition or omission of instruments in response to patient or physician feedback

## 5.22 Medical Chart Abstractions and Patient-Reported Medical Resource Utilization

### **5.22a Health/Treatment Information**

Participants' medical charts will be reviewed to abstract health and treatment related information, including disease site, comorbid health conditions, number of prior chemotherapy regimens, and time since diagnosis. Data will be recorded in the *Health/Tx Info* form (Appendix G).

### **5.22b Health Care Utilization**

Participants' medical charts will be reviewed to abstract health care utilization data during enrollment, including chemotherapy regimen and treatments, palliative care visits, emergency department visits, hospitalizations, and hospice referrals. If a participant dies while enrolled in the study, the date of death will also be recorded. Data will be recorded in the *Health Care Utilization* form

(Appendix H). Participants will also be given a patient diary to record all health care utilization that occurs during the study period, including hospitalizations, admissions to an intensive care unit, emergency room and urgent care visits, and oncology visits. This form was developed by the NRG Cancer Care Delivery Research Group because of a recognition that participants often receive care at outside hospitals that cannot be captured by abstracting the medical record. Clinical research coordinators will be asked to verify medical care that happened within a site-affiliated medical center. Participants' medical charts will be reviewed to abstract health care utilization data during enrollment, including chemotherapy regimen and treatments, palliative care visits, emergency department visits, hospitalizations, and hospice referrals. If a participant dies while enrolled in the study, the date of death will also be recorded. Data will be recorded in the Medical Resource Utilization Form (Appendix Z). Additionally, participants will be asked about whether they (or their informal caregiver) needed to take time off from work, how far they traveled for treatment, and for a rough estimate of their out-of-pocket expenditures to capture some of the burden associated with cancer care.

### **5.22c Call Log**

Per usual care, program nurses in the Division of Gynecologic Oncology will document participants' phone calls with clinical staff in participants' electronic medical health records. Study staff will abstract information about these phone calls during a participant's enrollment and record data in the *Call Log* (Appendix I). Data collected for each call will include: date/time, incoming/outgoing, left message, duration in minutes, reason for the call, symptoms documented, and the outcome.

### **5.23 Debriefing Interviews**

Debriefing interviews will be conducted with participants enrolled in the first phase and their oncology providers. The purpose of these interviews is to obtain information about the acceptability of the interventions and recommendations for modifications to improve any aspect of recruitment, enrollment, education, timing of study assessments, and the graphical display of information, the wearable accelerometers, and the smartphone app. We will also conduct debriefing interviews with a purposively sampled subset of patients enrolled in Phase II (see Appendix J: Debriefing Interviews for Phase 2). We will administer interviews to 5 patients enrolled in each arm of the study. We will aim to sample a subset of patients with varying backgrounds and experiences with the study in order to better understand how the HOPE trial interventions work across a diverse patient population.

Additionally, debriefing interviews will be audiotaped in order to ensure that the interviewer adequately captures all feedback from patients and caregivers. The consent forms for the study include information that the debriefing interview will be audiotaped, and we will verbally request permission from patients to audiotape the debriefing interview before beginning the interview. Verbal permission will be documented on RedCap in Appendix J: Debriefing Interviews for Phase 2. We will not administer a debriefing interview to any patient who does not consent to being audiotaped during the debriefing interview. All audio recordings of study sessions will be stored in secure locations in restricted-access, locked filing cabinets on Dana 10 and 11, and in password-protected folders on Partners servers. Recordings will be tied only to a study ID number, and the only document linking the patient's study ID to identifiable information is in a restricted-access, password-protected file stored securely on Dana-Farber servers. Audiotapes of debriefing interviews will be transcribed for further analysis using a DFCI-approved, HIPAA-compliant transcription vendor. All patient identifiable information will be removed when the audio recordings are transcribed. Audio recordings of debriefing interviews will be destroyed when analyses are complete.

### **5.3 Description of Interventions**

Per the protocol schema, the first phase of the study will test the HOPE app with the Fitbit Zip or the Fitbit Charge 2. Based on the usability and acceptability data, the larger pilot RCT will test the HOPE app and the Fitbit model selected based upon user feedback. Based upon participant feedback (70% preferred Charge 2) from the first phase of the study, Phase II will test the HOPE app with the Fitbit Charge 2.

### 5.31 Monitored Wearable Accelerometer: Fitbit

The Fitbit Zip is a commercially available accelerometer that is worn on the hip and tracks users' steps, distance, calories burned, and active minutes. The accuracy of the step counts reported by Fitbit's hip-worn accelerometers have been validated against treadmill walking, other accelerometers, and an indirect calorimetry device. In addition, the Fitbit Zip was found to be the most valid device in a study that examined the validity and reliability of ten commercially available accelerometers for measuring step count against the gold standard devices used in laboratory and free-living conditions. One of the advantages of the Fitbit Zip is it runs off of a watch battery which only needs replacing every 2-3 months. One of the disadvantages to using the device in free-living conditions is it may be difficult to distinguish between low activity levels and low adherence to the device.

The Fitbit Charge 2 is an accelerometer that is worn on the wrist and tracks users' heart rate continuously in addition to steps, distance, calories, and active minutes. The addition of an optimal heart rate sensor enables monitoring of the time that the tracker is being worn (e.g., adherence). Wrist-worn activity trackers have been shown to accurately measure heart rate when compared with electrocardiography, have good test-retest reliability (intraclass correlations of 0.75-0.95) but over count steps compared with the gold standard ActivPAL in free-living conditions due to the variability in limb-specific activities. One of the advantages of the Fitbit Charge 2 is it allows for close monitoring of adherence to the device over time because of its continuous measurement of heart rate. The disadvantages include: it is not as accurate as a hip-worn device, is dependent upon the user to recharge it every 3 days, and may be less accurate if the participant is dependent upon a device for ambulating (e.g., cane or walker) or wears the device on her non-dominant arm.

Fitbit data will be stored with Fitabase, (Small Steps Labs LLC), a third-party research platform designed to collect data from the Fitbit (<https://www.fitabase.com>). It provides minute-by-minute measures (e.g. steps, heart rate) for data monitoring and analysis. All data will be anonymized with the use of participant codes, and the data will be stored in a high security data center.

### 5.32 Smartphone Application: HOPE App

The other intervention is an iOS and Android smartphone application that runs on participants' personal smartphones and collects information about their health and behaviors. Originally named "Beiwe," the app was conceived and designed by one of the co-investigators, [name], at the Harvard T.H. Chan School of Public Health. Zagaran, Inc., located in Cambridge, Massachusetts, built the software.

In a prior pilot study, [name] tested the app in 13 patients with major depressive disorder. Participants installed the app on their personal smartphones and completed a self-report survey of PHQ-9 items 3 times per day with >75% adherence to the app over a 30-day period. Participants scores were strongly correlated with paper-based surveys administered in clinic (Pearson linear correlation coefficient 0.84) but were 3.0 points higher on average (i.e. indicating more distress), and participants were much more likely to report significant suicidal ideation.

Since this publication, [name] lab has developed a more sophisticated system that features a web-based research study portal, a customizable Android and iOS smartphone app, Amazon Web Services S3 database, and data modeling and analysis tools. The app collects many different types of sensor data and administers surveys. Although this platform has not yet been used in cancer patients,

there are currently 8 IRB approved protocols across local centers that are utilizing the Beiwe application in research, including Beth Israel Deaconess Medical Center, Harvard University (Faculty of Arts and Sciences), McLean Hospital, and Massachusetts General Hospital. Three studies have begun enrolling patients or healthy controls, and the user experience has been overwhelmingly positive. In addition, there are no signs that adherence is condition-specific to date.

In this study, the active smartphone app is named the “Helping Our Patients Excel (HOPE)” app.

### **5.32a. App Versions (Active vs. Passive)**

The HOPE Trial will employ two different versions of the customized smartphone app: an “active” app and a “passive” app.

Active app: The “active” app collects **both active and passive data** from the participant’s phone usage. Active data is collected while a patient is using the app (e.g. responding to survey questions). Passive data is collected continuously without patient input. Patients using the active app will be asked to actively respond to survey questions including the symptom survey and cancer experience question.

Passive app: The “passive” app collects **passive data only** from the participant’s phone usage. It does NOT collect active data (e.g, the participant will not be asked to respond to any survey questions.) The passive data collection will occur in the background of the phone.

As noted above, both the active app and passive app collect passive data from the participant’s phone. Specifically, as detailed in the *HOPE App Data Privacy and Security* (Appendix L), passive data includes: mobility traces, consisting of flights (linear segments of movement) and pauses (times of no movement) which are constructed from GPS data; and summary statistics of phone communication (calls and text messages) patterns, simple examples being the total number of communication events in a time period (e.g., 1 week), the total number of communication partners, reciprocity of communication (defined as the difference between outgoing communication volume and incoming communication volume).

The active and passive app are built on the same underlying platform (Beiwe). As such, the active and passive app have identical data security protections, which are detailed in Appendix L, HOPE App Data Privacy and Security.

### **5.32b Software and Data Collection Features**

The smartphone apps employ the original features and data collection methods used in the aforementioned studies and protocols. Consult *HOPE App Features and Screenshots* (Appendix K) for descriptions of the app’s features, including: log-in screen, “Call My Clinician” button, “Forgot Password” button, notifications, surveys, “Call Research Assistant” button, and main menu.

### **5.32c Symptom Management**

The active smartphone app is designed to collect and assess participants’ toxicities and symptoms on chemotherapy treatment in between visits with their clinician. Participants report the severity of their symptoms via a brief in-app survey of PRO-CTCAE items. The app then determines a symptom’s risk level and necessary response, which is either to provide no intervention, tailored symptom management advice, or an alert to call the clinician. Figure 3 provides a more detailed overview of this process.

[figure not shown]
The symptom response criteria and the *Symptom Management Content* (Appendix M) were developed by research staff in cooperation with the gynecologic oncology providers and staff nurses at Dana-Farber. The study PI, who is also a practicing gynecologic oncologist on the gynecologic oncology team, collated reputable and trusted sources, such as ASCO, the National Cancer Institute, and Dana-Farber, to create the content for each symptom, which includes: symptom management advice and questions to ask the clinical team. The content and response criteria were then reviewed and refined by study investigators, research staff, and gynecologic oncology clinicians to produce the final versions.

### **5.33 HOPE Symptom Education Website**

In Phase II of the study, participants randomized to receive the Fitbit+active app, or active app arms will have access to a website ([www.hopetrial.org](http://www.hopetrial.org)) which will contain static patient education materials about the symptoms that are targeted in the HOPE app. This website will present evidence-based information on symptom education and symptom management. Some of the content on the website will mirror the content in the symptom management app, while other information will be housed only on the website. The purpose of the website is to provide a centralized location for patients to find symptom education and symptom management information at any time they might be experiencing low-level symptoms. Content will be created by the study PI (a practicing gynecologic oncologist at DFCI) and the study team, and will include information from trusted sources such as the NCI and ASCO.

### **5.34 Encouragement to Wear Smartphone**

In Phase II of the study, participants will be randomized both to a main study arm and a secondary randomization. The secondary randomization will randomize patients either to be encouraged to wear the smartphone at all times during the study (n=50), or not encouraged to wear the smartphone at all times during the study (n=50). Participants who are randomized to the “encouraged” arm will receive an appliance (e.g belt clip/arm band) which will allow them to carry their smartphone with them throughout the day, including while they would not ordinarily carry their smartphones with them (such as when walking around inside the home.) Participants who are randomized to the “not encouraged” arm will not receive any instructions about keeping their smartphone with them, and will not be provided with an appliance to carry their phone throughout the day.

**Figure 3.** Symptom classification and response in the *active* smartphone app intervention

## 5.4 Data Collection

Tables 2 and 3 specify the instrument and intervention data collection timelines during each study phase. Intervention data will be collected continuously during enrollment; all sync automatically over Wi-Fi.

**Table 2. First phase instrument data collection**

INSTRUMENT		DAY		
		Visit 0	1-29	Visit 30
	Participant Baseline Interview	✓		
	Participant Post-Baseline Interview			✓
	Clinician Survey	✓		✓
	Debriefing Interviews			✓
	Accelerometer Data		✓	✓
	Daily QoL, PF, and Symptom Questions		✓	
	Weekly Symptom Survey		✓	
	Passive App Data		✓	✓

**Table 3. Second phase RCT instrument data collection per study arm**

INSTRUMENT		DAY						
		Visit 0	1-29	Visit 30	31-89	Visit 90	91-179	Visit 180
	Participant Baseline Interview	1,2,3,4						
	Participant Post-Baseline Interview			1,2,3,4		1,2,3,4		1,2,3,4
	Clinician Survey	1,2,3,4		1,2,3,4		1,2,3,4		1,2,3,4
	Health/Tx Info	1,2,3,4		1,2,3,4		1,2,3,4		1,2,3,4
	Healthcare Utilization			1,2,3,4		1,2,3,4		1,2,3,4
	Call Log			1,2,3,4		1,2,3,4		1,2,3,4
	Accelerometer Data		1,2	1,2	1,2	1,2	1,2	1,2
	Daily Quality of Life, Physical Function, and Symptom Questions		1,3	1,3	1,3	1,3	1,3	1,3
	Weekly Cancer Experience Question	1,3	1,3		1,3		1,3	
	Weekly Physical Function Survey		1,3	1,3	1,3	1,3	1,3	1,3

1. Fitbit + active app

2. Fitbit + passive app

3. Active app

4. Passive app

Data obtained via interviews, surveys and chart abstractions will be stored on the Harvard REDCap server. HOPE App will employ the same data privacy and security processes used in six IRB approved protocols across three Partners Institutions (BIDMC Protocol #: 2015P-000240; McLean Hospital Protocol #: 2015P001303, 2015P001538, 2012P000890, 2015P002189; MGH Protocol #: 2015P000666). Although the app collects a large amount of data, it was custom built to be used in a health care setting and includes robust security and privacy features to safeguard all data and protect participants' privacy, including data anonymity, participant authentication, and data encryption. Hope App Data Privacy and Security describes the processes in detail.

Fitbit data will be stored with Fitabase, a research platform that collects and stores data from Internet connected devices, like Fitbit, for monitoring and analysis. It provides minute-by-minute measures (e.g. steps, heart rate) for data monitoring and analysis. All data will be anonymized with the use of participant codes, and the data will be stored a in high security data center.

## **5.5 Description of Study Process**

Study procedures for the first phase are outlined below. Prior to opening the second phase, the study protocol and procedures will be amended based upon participant and clinician feedback. The RA will be primarily responsible for carrying out the following procedures; study staff will be trained accordingly so they can perform procedures as needed.

Based on the study team's experience conducting pilot studies, we understand that piloting minimal-risk interventions must be flexible in order to ensure that they can quickly adapt to patient needs as we learn more about them over the course of the study. The study activities currently outlined in the protocol therefore may be adapted without the submission of an amendment in cases where these modifications would pose no additional risk to patients, as determined by the study PI.

### 5.5.1 Instrument Administration

#### Participant Baseline Interview:

- The RA will administer the survey to participants via an in-person interview on Day 0 before or after the participant's visit with her oncology provider (Baseline Visit).
- Participants will complete the interview on the same day informed consent is obtained; if this is not possible, the RA and participant will plan to complete it at a subsequent visit.
- Participants will not be asked to come to Dana-Farber outside of their regularly scheduled visits.
- Estimated time to completion: 45 minutes.

#### Participant Post-Baseline Interview:

- The RA will administer the interview to participants via an in-person interview before or after a regularly scheduled visit that falls as close to the projected assessment date as possible (Post-Baseline Visit).
- Every effort will be made to administer the interview in-person and on the date of the Post-Baseline Visit. If this is not feasible, participants will complete it over the phone as close to the visit date as possible.
- To encourage participation and reduce the number of incomplete interviews, participants will be contacted prior to their visit to confirm the date of their upcoming visit and interview.
- Estimated time to completion: 30 minutes.

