#### **5.21a Global Health Status: EQ-5D-5L**

The EQ-5D is a standardized measurement of health status that has been used in a wide range of health conditions and treatments, including cancer patient populations. The EQ-5D-5L is the most recent 5-level version that has proven validity and reliability in a range of patient groups with chronic diseases and cancer. It is a 5-item questionnaire (measuring mobility, self-care, usual activities,

pain/discomfort, and anxiety/depression. Each dimension has three levels of perceived problems: 1) no problems, 2) slight problems, 3) moderate problems 4) severe problems, and 5) extreme problems. Patients check the statement level that best describes their current health status in each dimension, which are then scored to generate a patient's unique health state. In the EQ-VAS, patients report a single index value of how good or bad their current health state is on a visual scale that ranges from worst imaginable at zero to best imaginable at one hundred. The EQ-5D-5L can be administered with little to no guidance and takes only a few minutes to complete. Upon scoring, the EQ-5D produces a composite score between 0-1 (multiplied by 100 to generate a number between 0-100), which represents general health status, normalized for the US population. Lower scores represent worse quality of life, and a change of  $\geq 6$  is clinically significant in US cancer populations.

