### **5.21n Cancer Experience Question**

#### *About the cancer experience question*

On a weekly basis, participants will be asked one qualitative question about their cancer experience. We hope that this open-ended question will give patients an opportunity within the study to express additional concerns, emotions and experiences regarding their cancer that may not be adequately reflected in other study instruments. A large body of previous work has successfully asked cancer patients to share open-ended, qualitative measures of their emotional experiences (i.e. by writing in response to a prompt). However, to our knowledge, our study will be the first to examine whether these qualitative measures correspond with clinical outcomes measured in real time in the real world.

Using a question adapted from Stanton and colleagues' emotional expression study with breast cancer survivors, participants will be asked to describe their experience with cancer over the course of the previous week. Participants will be presented with the cancer experience question as an audio survey within the HOPE App once a week (see Appendix F for question text) and will record their answers into the microphone of their smartphone. The app reminds the participant to make a voice recording in the same way that it reminds the participant to take any other survey in the HOPE app: by making a notification appear in the phone. The participant does not need to make a voice recording immediately and may wait until she is in private to do so. The participant can make the audio recording in the app at any time after the notification appears, until the next audio recording reminder replaces it. Participants will spend up to 5 minutes on this question, depending on how much they wish to share. This question will be answered within the smartphone app at the baseline interview and symptom survey (once weekly).

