#### Instructional Session:

- Following the completion of the Participant Baseline Survey on Day 0, the RA will help participants' download the Fitbit software and smartphone app, demonstrate how to use the Fitbit app and device, and teach patients how to synch the device to their smartphone. Participants will be assigned a unique study email that will be used to synch the device with the Fitbit app, as well as register the device in Fitabase (i.e., study's data collection platform).
- To reduce missing data, the RA will highlight the importance of wearing the accelerometer and review how they will be contacted by the study team, ideally through their preferred method of communication (phone/text/email), to encourage compliance. In addition to the accelerometer, participants will receive a wireless sync connector, and the *Fitbit Participant Guide* (Appendix Q), which describes proper wear and care, charging and battery life, troubleshooting instructions, uploading data, and compliance.
- The RA will encourage participants to contact study staff at any time with questions or issues to help ensure proper wear and use of the Fitbit.

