#### Primary Endpoint: Second Phase

- 1) Health-related quality of life, comparing the patient-reported baseline and 6-month EuroQol EQ-5D.

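### In HOPE Phase 2 the primary EQ-5D is taken by interview by the staff role that teaches the intervention, before or after an arm-dependent clinic visit, which opens an avoidable route for reporting bias

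*Combined protocol and SAP*

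**What the plan says.** Section 6.1 of the HOPE protocol names one Phase 2 primary endpoint: "Health-related quality of life, comparing the patient-reported baseline and 6-month EuroQol EQ-5D". Table 1 places the EQ-5D-5L in the participant baseline and post-baseline interviews, and Table 3 schedules the latter at days 30, 90 and 180 in all four arms.

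Section 5.5.1 sets out how these are done. At baseline, "The RA will administer the survey to participants via an in-person interview on Day 0", before or after the oncology visit. At follow-up, "The RA will administer the interview to participants via an in-person interview before or after a regularly scheduled visit", or by telephone if that is not feasible. Section 5.21p confirms that an RA administers these surveys.

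The same role has other duties. Section 5.5 states: "The RA will be primarily responsible for carrying out the following procedures". Under 5.52a the RA reviews use of the app with an arm-specific guide and contacts patients when it fails to sync. Under 5.52b the RA teaches the Fitbit (arms 1 and 2), follows up its sync failures, and "the RA will highlight the importance of wearing the accelerometer".

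Section 5.52a also has patient and provider receive a summary around each visit: symptoms, steps or both in arms 1 to 3, and none in arm 4. Sections 4.2 and 6.3 describe sealed envelopes for allocation. No section describes blinding after assignment.

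On the instrument itself, section 5.21a says: "The EQ-5D-5L can be administered with little to no guidance and takes only a few minutes to complete".

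**The concern.** The trial is open-label and the endpoint is a subjective score, so some reporting bias from the patient's knowledge of her arm cannot be avoided. The plan adds a second route that can be. By default a patient tells the role that taught her the intervention, and may have contacted her about missing data, how well she is. That role cannot be unaware of her arm.

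Timing adds to this. The interview may fall on either side of a visit at which arms 1 to 3 may be shown their summaries and arm 4 is not. The protocol neither fixes the order nor asks for it to be recorded.

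At stake is the decision in section 6.2, where a one-sided 5% test decides whether an intervention is promising for further study. A shift in reporting that differs by arm would enter that test directly, and the analysis could not separate it from a real effect.

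**Working it through.** **Inputs.** Section 6.2: SD of change 14; 25 per arm; one-sided 5%. Section 6.4: each factor is tested at its margin, with Fitbit as arms 1+2 v 3+4 and active app as arms 1+3 v 2+4, so 50 v 50.

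**Standard error.** SE = 14 × √(2/50) = 2.8 points.

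**Reproducing the plan's power.** Power = Φ(δ/2.8 − 1.645).
- δ = 6: Φ(2.143 − 1.645) = 69.1% (stated 70%).
- δ = 7: Φ(2.5 − 1.645) = 80.4% (stated 80%).

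The remaining rows of the power table also reproduce to within 2 percentage points, so the design figures are not in dispute.

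**From a shift in some arms to a shift in the test.** Suppose, as an assumption, that reporting is shifted by b points in arms 1, 2 and 3 relative to arm 4.
- Fitbit margin: (b + b)/2 − (b + 0)/2 = b/2.
- App margin: (b + b)/2 − (b + 0)/2 = b/2.

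Each comparison group contains one shifted arm, so only half the shift reaches either contrast.

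**Chance of a false conclusion with no true effect.** Error = 1 − Φ(1.645 − m/2.8), where m is the shift in the contrast.

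| Assumed b (points) | m = b/2 | Error | Error if the full b fell along one factor (m = b) |
|---|---|---|---|
| 0 | 0 | 5.0% | 5.0% |
| 1 | 0.5 | 7.1% | 9.9% |
| 2 | 1.0 | 9.9% | 17.6% |
| 3 | 1.5 | 13.4% | 28.3% |

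The last column would need, for example, a shift in both active-app arms and in neither passive-app arm. The values of b are assumed. A shift in the unfavourable direction would lower power instead.

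**The case against.** Several points on the other side stand.

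- **Arm 4 also has RA contact.** The teaching and sync-contact parts of 5.52a cover both app versions. Arm 4 lacks the Fitbit steps and the active-app content, so contact is plausibly lighter, but by an amount the documents do not give.
- **Direction is open.** A reader might infer that the bias must favour the intervention. Daily symptom questions could equally make active-app patients report more problems.
- **The PHQ-9 result is not interviewer evidence.** Section 5.32 reports that app scores were strongly correlated with clinic paper scores "but were 3.0 points higher on average (i.e. indicating more distress". A reader might take this as proof that the interview biases the endpoint. It compares app with paper in 13 patients and involves no interviewer, and a mode effect common to all arms would cancel.
- **Baseline comes before device set-up.** Sections 5.52a and 5.52b place app and Fitbit set-up after the baseline survey. Of the cancer experience question, which Table 3 gives only to arms 1 and 3, section 5.21n says: "This question will be answered within the smartphone app at the baseline interview and symptom survey (once weekly". A reader might infer that the arm was known when the baseline EQ-5D was answered. Since the app is installed after the survey, that does not follow. What is unstated is when the envelope is opened, and the schema figure, not available here, may settle it.
- **Visit timing is partly common to all arms**, and summaries may go by email.
- **The same person is the default, not a certainty.** Section 5.5 lets other trained staff perform procedures.
- **RA administration has uses**: immediate sight of PHQ-9 answers (5.21p) and, through the pre-visit contact, fewer incomplete interviews (5.5.1).
- **The endpoint is already described as patient-reported**, with patients ticking the statements (5.21a). Appendices C and D, which hold the forms, are not available. If self-completion is intended, 5.5.1 should say so.

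Section 5.5 introduces its procedures as first-phase. However, it contains Phase 2 arm-specific text and no other Phase 2 interview procedure is given, so it is the operative text.

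**Conclusion.** The concern holds as an avoidable weakness in how the sole primary endpoint is collected. It does not show that the result will be biased. That the interviewer knows the arm is an inference from the RA's duties, but a firm one, since no separation of roles is described.

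Size and direction are not in the documents. If reporting were shifted favourably by 1 to 3 points in arms 1 to 3 relative to arm 4, the false-positive rate for each factor would be about 7% to 13% instead of 5%. A reader might apply the same shift to the whole contrast and quote 10% to 28%. That requires a full shift along one factor, which the RA's role across arms 1 to 3 does not imply. None of these figures separates the part due to the interviewer from the part due to the patient's own knowledge of her arm.

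The change is worth making because it is cheap and the endpoint is the only primary one.

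**What to change.** In section 5.5.1:

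1. State that the EQ-5D-5L is completed by the patient herself (REDCap tablet or link, or paper) at baseline and at days 30, 90 and 180, before she sees the clinician or the summary sheet where feasible, with the RA giving technical help only.
2. Record the mode of each assessment and its timing relative to the visit.
3. State that the baseline EQ-5D is completed before the allocation envelope is opened.

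The PHQ-9 and the other measures can stay RA-administered, so the safeguard in 5.21p is unchanged.

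The cost is protocol wording and a REDCap survey setting. REDCap already stores the interview data, and section 5.5.1 already offers clinicians a REDCap survey or hard copy. The downsides are a few more skipped items and less scheduling flexibility. The change removes the assessor route only.
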